HILLCLIMBER is a randomized, controlled, open-label phase II trial of moderate dose statin therapy versus high-dose statin therapy in HIV-infected persons taking antiretroviral therapy (ART) who have coronary heart disease (CHD) or are at high risk for atherosclerotic cardiovascular disease. All subjects will have an initial two-week run-in period with pravastatin 40mg daily. Subjects not demonstrating significant toxicity at week 2 will then be randomized to rosuvastatin 20mg versus continuing pravastatin 40mg daily. At week 6; those in the rosuvastatin arm who do not demonstrate significant clinical or laboratory safety/toxicity issues will then have doses increased to rosuvastatin 40mg (high intensity dose group). The group randomized to pravastatin 40mg daily at week 2 will not have their dose increased at the end of week 6 (moderate intensity group).

- The primary endpoint is percent change in low-density lipoprotein cholesterol (LDL-c) from Week 2 to 14 of high versus moderate intensity lipid-lowering statin therapy

DURATION

Total duration of the study is 14 weeks: 2 weeks for the initial run-in, 12 weeks on therapy as per randomization (weeks 6-14 with possible dose increase).

SAMPLE SIZE

40 subjects

POPULATION

HIV-infected subjects not already on high dose statin therapy who have coronary heart disease (CHD) or are at high risk for atherosclerotic cardiovascular disease (ASCVD, which includes myocardial infarction and stroke) as evidenced by 10-year ASCVD risk of 15.0% or greater.

REGIMEN

The following treatment regimens will be used:

Stage One (Run-in): Pravastatin 40mg daily (Weeks 0-2),

Stage Two (Randomization in 1:1 ratio):

- Moderate intensity group: Pravastatin 40mg daily (Weeks 2-14)

OR

- High intensity group: Rosuvastatin 20mg daily (Weeks 2-6), titrated to Rosuvastatin 40mg daily (Weeks 6-14).

1.0 STUDY OBJECTIVES

1.1 Primary Objectives

- To evaluate the lipid-lowering efficacy, as measured by percent change in low-density lipoprotein cholesterol (LDL-c) from Week 2 to 14 of high versus moderate intensity lipid-lowering statin therapy in HIV-infected persons taking antiretroviral therapy (ART)

who have coronary heart disease (CHD) or are at high risk for atherosclerotic cardiovascular disease (ASCVD).

1.2 Secondary Objectives

To determine mean changes from week 2 to week 14 for patients randomized to high versus moderate intensity statins in the following:

- Lipid parameters (HDL-c, triglycerides, and total cholesterol)
- Inflammatory biomarkers (soluble CD163, ST2, high sensitivity troponin I, and high-sensitivity C-reactive protein)
- Immunologic markers (T cell reactivity) and viral reservoir persistence

To evaluate safety, as measured by treatment-emergent clinical and laboratory adverse events, of high versus moderate intensity statin therapy in HIV-infected persons taking ART who have coronary heart disease (CHD) or are at high risk for ASCVD.

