9.2.2 Secondary Endpoints

Secondary endpoints include mean percent changes in the following from week 2 to week 14:

- Lipid parameters (HDL-c, triglycerides, and total cholesterol),
- Inflammatory biomarkers (soluble CD163, ST2, high sensitivity troponin I, high-sensitivity CRP, PAI-1, Lp-PLA2)
- Viral and immunologic markers derived from PBMCs (such as T cell reactivity and viral reservoir persistence).
- Statin drug levels >400% expected steady-state dose level
- Hemoglobin A1c level

An additional secondary endpoint will evaluate safety, as measured by treatment-

emergent clinical and laboratory adverse events, of high versus moderate intensity statin therapy in HIV-infected persons taking ART who have coronary heart disease (CHD) and/or 15% or greater risk for ASCVD.

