9.6.2 Secondary Analyses

Safety and tolerability data will be summarized by treatment group.

Adverse events (signs, symptoms, and diagnoses) will be analyzed and reported using the AIDS Clinical Trials Group (ACTG) medical dictionary and standardized coding for Signs, Symptoms, and Diagnoses for Clinical and Adverse Events. Adverse events will be tabulated by treatment group and will include the number of patients for whom the event occurred, the rate of occurrence, and the severity and relationship to study drug.

Incidence of clinical and/or laboratory toxicities. The safety and tolerability measures will include:

- Time to discontinuation of any study medication due to adverse events (AEs), --
- Proportion of Grade 3 or Grade 4 clinical AEs,
- Proportion of Grade 3 or Grade 4 laboratory abnormalities,
- Summaries of all treatment-related AEs

Possible future analyses

- Measures of the HIV reservoir size
- Soluble and cellular markers of immune activation and inflammation

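### Secondary lipid and biomarker endpoints are stated on two scales with no analysis method; fix one definition per marker, with week-2-adjusted log-scale ANCOVA for markers expected to be right-skewed

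*Combined protocol and SAP*

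**What the plan says.** Section 1.2 introduces the secondary objectives with "To determine mean changes from week 2 to week 14", for the high against the moderate intensity arm. The list covers "Lipid parameters (HDL-c, triglycerides, and total cholesterol"), "Inflammatory biomarkers (soluble CD163, ST2, high sensitivity troponin I, and high-sensitivity C-reactive protein"), and T cell and viral reservoir measures. Percent is not mentioned.

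Section 9.2.2 says "Secondary endpoints include mean percent changes in the following from week 2 to week 14". It repeats the lipids but widens the marker list to "Inflammatory biomarkers (soluble CD163, ST2, high sensitivity troponin I, high-sensitivity CRP, PAI-1, Lp-PLA2"). It also places haemoglobin A1c and a drug-level threshold (above four times the expected steady-state level) under the same mean-percent-change heading.

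Section 9.6.2, on secondary analyses, opens with "Safety and tolerability data will be summarized by treatment group" and then covers adverse events and tolerability. It names no test, scale, transformation or model for the secondary lipids or biomarkers. "Soluble and cellular markers of immune activation and inflammation" appears there only among analyses that might be done later. The two-sample t-test in the plan is in section 9.6.1, for the primary LDL-c endpoint.

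**The concern.** Mean change and mean percent change are different estimands, and an effect can look different on each. Triglycerides, hs-CRP, troponin and soluble markers are positive quantities that one would expect to be right-skewed. For such data the mean absolute change is dominated by patients with high week-2 values, and the mean percent change is pulled up by patients with low ones. With 15 to 25 patients per arm, the choice of scale can decide whether a real effect is detected. It can also decide the apparent direction of a small effect. The trial is open-label and describes itself as a pilot for later studies, so an effect estimate with one clear, pre-stated meaning is worth having.

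**Working it through.** **The plan's own figure.** The only sample-size calculation (section 9.4) is for LDL-c: difference 25 mg/dl, SD 20, two-sided alpha 0.05, power 0.80. By the normal approximation, n per arm = 2 × (1.96 + 0.84)² × 20² / 25² = 10.05, rounded up to 11. It reproduces the stated figure, but says nothing about the secondary endpoints, which have no sample-size or power statement.

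**Inputs.** Total enrolment is 40 in sections 3.0 and 9.1, and 30 with up to 50 in section 9.4. At 1:1 that is 15 to 25 per arm; 20 is used below. The documents give no SD, skewness, correlation or effect for any secondary marker, so the following are assumptions:
- week-2 and week-14 values bivariate lognormal, log-SD 0.5, 0.8 or 1.0
- correlation 0.6 on the log scale
- true ratio 0.6 between arms (a 40% lower marker)
- two-sided alpha 0.05

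**Simulated power, 20 per arm.** The first three methods are two-sample t-tests. The fourth is ANCOVA of the log week-14 value on the log week-2 value.

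| log-SD | absolute change | percent change | log ratio | log ANCOVA |
|---|---|---|---|---|
| 0.5 | 0.78 | 0.92 | 0.94 | 0.97 |
| 0.8 | 0.34 | 0.50 | 0.59 | 0.68 |
| 1.0 | 0.20 | 0.31 | 0.42 | 0.50 |

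**Where the gain comes from (log-SD 0.8).** ANCOVA on the raw scale has power 0.52.
- From absolute change: adjustment adds 0.52 − 0.34 = 0.18, and the log scale adds 0.68 − 0.52 = 0.16.
- From percent change: the log scale adds 0.59 − 0.50 = 0.09, and adjustment adds 0.68 − 0.59 = 0.09.

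**When skew is mild or absent (20 per arm, correlation 0.7).**

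| Scenario | absolute | percent | log ratio | log ANCOVA | raw ANCOVA |
|---|---|---|---|---|---|
| lognormal, log-SD 0.25, ratio 0.8 | 0.90 | 0.94 | 0.94 | 0.97 | 0.96 |
| normal, CV 0.25, additive −20% | 0.89 | 0.87 | 0.89 | 0.90 | 0.93 |
| normal, CV 0.25, additive +20% | 0.89 | 0.78 | 0.82 | 0.91 | 0.93 |

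The unadjusted log ratio can lose to absolute change (0.82 against 0.89). In the two additive cases raw ANCOVA beats log ANCOVA by 2 to 3 points. Log ANCOVA is not below either of the plan's scales in any scenario run.

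**Disagreement between the plan's two scales.** With correlation 0.6 and a true 20% reduction, the between-arm differences in absolute change and in percent change had opposite signs in 6% of simulated trials at log-SD 0.5, 18% at 0.8 and 24% at 1.0.

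**No true effect.** The expected within-arm mean percent change is exp(log-SD² × (1 − correlation)) − 1. At log-SD 0.8 this is exp(0.64 × 0.4) − 1 = 0.29, or +29%, in both arms alike. The between-arm difference stays at about zero. At log-SD 1.0 and correlation 0.7, t-tests on absolute and percent change rejected in 3.4% to 4.4% of null trials, so type I error is not inflated.

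**What the schedule allows.** Section 6.1 has fasting lipids and stored plasma and serum at both week 2 and week 14, so week-2 adjustment needs no new data. Haemoglobin A1c is scheduled only at weeks 0 and 14, so its change from week 2 cannot be computed.

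**The case against.** The strongest reply is that section 9.2.2 is the statistical definition, that percent change there matches the primary endpoint, and that 1.2 is only looser wording. On that view there is no open choice, and 9.6.2 and the stored-sample section (6.3.8) leave the markers for later anyway. These are also unpowered secondary endpoints in a pilot. This is a fair argument for modest severity. It does not supply an analysis method, explain the differing marker lists, or make percent change efficient for skewed markers.

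A second reply is that a lognormal model with a ratio effect is the setting in which log analysis does best, so its advantage is partly built in. That stands: a reader might infer that the log scale is clearly stronger for every listed endpoint, and the documents do not support this. They report no distribution for any marker, no skew is shown for HDL-c or total cholesterol, and near-normal additive cases slightly favour the raw scale once both are adjusted.

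A reader might also take the +29% mean percent change under no effect as a route to a false finding. It is not one, because it arises in both arms and cancels in the randomised comparison. It would mislead only someone reading the within-arm means.

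**Conclusion.** The contradiction in scale, the mismatch in marker lists and the missing secondary efficacy analysis are on the page. For markers expected to be right-skewed, neither stated scale is efficient. Under the assumptions above, log ANCOVA gains about 5 points of power over percent change at log-SD 0.5, 18 at 0.8 and 19 at 1.0; over absolute change it gains 19, 34 and 30. Part of each gain is baseline adjustment rather than scale, and under mild skew the gain is small. The loss is in power and interpretability; false-positive risk is not raised. It would go too far to say that the scale will be picked after seeing results: the documents leave room for that but do not show it. This should be changed, but it touches secondary endpoints only.

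**What to change.** - Use the same marker list in sections 1.2, 9.2.2 and 9.6.2, and say whether the soluble inflammation markers are secondary endpoints or deferred work.
- Give one endpoint definition per marker, and add an efficacy analysis to 9.6.2: ANCOVA of the week-14 value adjusted for the week-2 value and the randomisation strata. The strata must first be reconciled, since section 4.3.2 names boosted ART only and section 9.3 adds known CHD.
- For triglycerides, hs-CRP, troponin and other positive markers expected to be right-skewed, analyse on the log scale and report a ratio of geometric means with 95% CI. State a rule for values below detection.
- For HDL-c and total cholesterol, either scale is acceptable with week-2 adjustment; name one in advance.
- Define haemoglobin A1c separately, since it has no scheduled week-2 value, and treat the drug-level threshold as a proportion rather than a mean percent change.

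The cost is wording. The week-2 and week-14 lipids and stored samples are already scheduled, but the objectives in 1.2 must be amended, so this is a protocol change as well as an analysis-plan one. Results for the skewed markers will be ratios of geometric means rather than simple averages.

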2.0 Background

This study is a phase II investigation of the efficacy of high intensity versus moderate intensity lipid lowering statin therapy for HIV-infected persons with coronary heart disease (CHD) and/or high risk for atherosclerotic cardiovascular disease (ASCVD) not already on high intensity lipid lowering therapy. This is a pilot study for potential future studies that would be adequately powered to evaluate the safety – in addition to efficacy – of high-intensity versus moderate-intensity statin regimens for HIV-infected persons with CHD and/or high risk for ASCVD. The study drugs (rosuvastatin and pravastatin) are approved and in regular clinical use, but rosuvastatin is being repurposed in this study for a new population in which there are no data for the higher intensity therapy under study.

2.1 Rationale

Over the past two decades, antiretroviral therapy (ART) has dramatically improved longevity among persons living with human immunodeficiency virus (HIV), who are increasingly at risk for non-communicable comorbidities such as cardiovascular disease (CVD). (1-5) Compared with uninfected persons, persons living with HIV are at 50% or greater risk for myocardial infarction (MI), even after adjustment for CVD risk factors, and over fourfold greater risk for sudden cardiac death. (6-13) Standard care for persons with coronary heart disease (CHD), which includes previous acute coronary syndromes (ACS) and MI, in the general population includes intensive lipid lowering with high dose statin therapy, such as rosuvastatin 20-40mg daily or atorvastatin 40-80mg daily, due to high-quality clinical trial data demonstrating significant net clinical benefits of intensive lipid lowering with high dose statins compared with less intensive lipid lowering with lower dose statins. (14-16) The importance of intensive lipid lowering following coronary events has been re-affirmed by a recent trial in which patients hospitalized for ACS randomized to a statin plus ezetimibe versus a statin alone achieved lower LDL-c levels (median LDL-c 53.7 mg/dl versus 69.5 mg/dl) and experienced improved cardiovascular outcomes without excess adverse events. (17) Furthermore, the most recent American College of Cardiology (ACC)/American Heart Association (AHA) evidence-based guidelines recommend that persons with predicted 10-year ASCVD risks of 7.5% or greater be prescribed moderate-to-high-intensity statins; the absolute net benefit of intensifying statin

therapy becomes even greater and thus favors high intensity statin therapy at higher ASCVD risk levels. (18)

Despite these convincing data in the general population, it remains unknown whether intensive lipid lowering with high dose statins for HIV-infected persons with known CHD and/or high risk for ASCVD confers clinical benefit. Trials of lipid-lowering therapy among persons living with HIV on ART have generally tested lower dose statins due to safety concerns related to theoretical and observed drug-drug interactions between ARTs, particularly protease inhibitors (PIs), and statins. Some of this is warranted; simvastatin is contraindicated with concomitant PI use and should generally be avoided in patients on ART, as simvastatin levels increase more than fivefold with concomitant PI use. (18) However, most other statins have proven safe and efficacious in numerous small trials of HIV-infected persons on ART, albeit at relatively low doses. (19) The most potent statin doses tested in these trials have generally been rosuvastatin 10mg daily or atorvastatin 10mg daily (20-24); a lone exception is a recent trial in which 19 HIV-infected persons were started on atorvastatin 20mg daily and titrated up to 40mg daily, which revealed similar safety profiles of atorvastatin 40mg daily and placebo. (25) No trials of any size have evaluated HIV-infected persons on ART taking atorvastatin 80mg daily or rosuvastatin 20-40mg daily, which are the standard of care for persons with CHD, particularly previous ACS, as well as persons with high ASCVD risk, in the general population.

In this study, we intend to evaluate high intensity rosuvastatin (20mg daily uptitrated to 40mg daily) rather than atorvastatin 80mg daily because rosuvastatin 40mg daily has somewhat greater LDL-lowering efficacy and fewer pharmacological interactions with common HIV medications, particularly protease inhibitors. Rosuvastatin is not lipophilic, absorbed rapidly, and minimally (<10%) metabolized by the CYP450 system, resulting in negligible pharmacokinetic interactions with protease inhibitors or other CYP450-metabolized medications; meanwhile, atorvastatin is more lipophilic and metabolized extensively by the CYP450 system, resulting in potential toxicity due to accumulation in the setting of co-administration with protease inhibitors and other CYP450-metabolized medications. (26) Thus, although rosuvastatin and atorvastatin both appear to be safe based on limited data in HIV-infected persons taking ART, we anticipated that the safety margin would be greater for high-dose rosuvastatin compared with atorvastatin in this population. This a randomized, controlled, open-label Phase II study of a known approved drug re-purposed for a unique population.

Full prescribing information for rosuvastatin, which is an approved drug with tablets of doses 5mg, 10mg, 20mg, and 40mg, may be found at: <http://www1.astazeneca-us.com/pi/crestor.pdf>. Full information for pravastatin, which is an approved drug with tablets of doses 10mg, 20mg, 40mg, and 80mg, may be found at: http://www.accessdata.fda.gov/drugsatfda_docs/label/2012/019898s062lbl.pdf.

3.0 STUDY DESIGN

This is a single center, randomized, controlled, open-label phase II trial. Up to 40 subjects not already on high dose statin therapy who have documented CHD and/or calculated 10-year ASCVD risk >15% will be included and started on moderate dose statin therapy (pravastatin 40mg daily) for an initial two-week run-in period. Subjects not demonstrating significant toxicity at week 2 will then be randomized to rosuvastatin 20mg versus continuing pravastatin 40mg daily. Subjects will return at week 6; those in the rosuvastatin arm who do not demonstrate significant safety or toxicity concerns will then have doses increased to rosuvastatin 40mg (high dose group). The group randomized to pravastatin 40mg daily at week 2 will not have their dose increased at the end of week 6.

The following treatment regimens will be used:

Stage One (Run-in): Pravastatin 40mg daily (Weeks 0-2),

Stage Two (Randomization in 1:1 ratio):

- Moderate intensity group: Pravastatin 40mg daily (Weeks 2-14)
OR
- High intensity group: Rosuvastatin 20mg daily (Weeks 2-6), potentially titrated to Rosuvastatin 40mg daily (Weeks 6-14).

Total duration of the study is 14 weeks: 2 weeks for the initial run-in, 6 weeks following randomization, and 6 weeks following dose increase.

4.0 SELECTION AND ENROLLMENT OF SUBJECTS

4.1 Inclusion Criteria

- 4.1.1 HIV-1 infection, documented by: any licensed rapid HIV test or HIV enzyme or chemoiluminescence immunoassay (E/CIA) test kit at any time prior to study entry and confirmed by a licensed Western blot or a second antibody test by a method other than the initial rapid HIV and/or E/CIA, or by HIV-1 antigen or plasma HIV-1 RNA viral load. OR HIV-1 RNA detection by a licensed HIV-1 RNA assay demonstrating >1000 RNA copies/mL
- 4.1.2. HIV RNA below the lower limit of assay detection within 12 months of study entry
NOTE: one detectable HIV RNA (<400 copies/ml) is allowed.
- 4.1.3 (1) Documented coronary heart disease (CHD): nonfatal MI, unrecognized MI, unstable angina pectoris, and/or stable angina pectoris, as defined by the American Heart Association Case Definitions for Acute Coronary Heart Disease in Epidemiology and Clinical Research Studies (Luepker R et al., Circulation 2003. 108(20):2543-9. URL: <http://circ.ahajournals.org/content/108/20/2543>).
Or (2) Documented 10-year ASCVD risk of 15% or greater based on the ACC/AHA ASCVD Risk Estimator (<http://tools.acc.org/ASCVD-Risk-estimator/>).
- 4.1.4 Negative serum or urine pregnancy test within 48 hours of study entry for women with reproductive potential (defined as women who have not been postmenopausal for at least 24 consecutive months, i.e., who have had menses within the preceding 24 months, or have not undergone surgical sterilization [e.g., hysterectomy, bilateral oophorectomy, or salpingectomy]). The urine test must have a sensitivity of ≤50 mIU/mL.
- 4.1.5 If participating in sexual activity that could lead to pregnancy, female subjects with reproductive potential must use one form of contraceptive as listed below while receiving protocol-specified medications. At least one of the following methods MUST be used appropriately:
 - Condoms (male or female) with or without a spermicidal agent. Condoms are recommended because their appropriate use is the only contraception method effective for preventing HIV transmission.
 - Diaphragm or cervical cap with spermicide

- IUD (intrauterine device)
- Hormone-based contraceptive. Subject-reported history is acceptable documentation of sterilization, other contraception methods, menopause, and reproductive potential.

4.1.6 Men and women age 18 to 75 years of age

4.1.7 Ability and willingness of subject to provide informed consent

4.2. Exclusion Criteria

- 4.2.1 Serious illness or AIDS-related complication within 21 days of screening requiring systemic treatment and/or hospitalization until candidate either completes therapy or is clinically stable on therapy, in the opinion of the site investigator, for at least 7 days prior to study entry. Need for systemic therapy for malignancy currently or anticipated during the study period.
- 4.2.2 No coronary heart disease (CHD) and 10-year ASCVD risk <15.0%.
- 4.2.3 Not currently receiving antiretroviral therapy or taking any of the following antiretroviral agents: atazanavir/ritonavir, lopinavir/ritonavir, or simeprevir.
- 4.2.4 Not currently receiving any of the following agents: cyclosporine or rifampin.
- 4.2.5 History of statin intolerance leading to discontinuation, dose decrease, or change to less potent dose equivalent
- 4.2.6 Statin absolute contraindication
- 4.2.7 Current use of atorvastatin 20mg daily or greater or rosuvastatin 10mg daily or greater
- 4.2.8 Chronic kidney disease stage 4 or greater (including dialysis)
- 4.2.9 Systolic heart failure with last documented LVEF <35%
- 4.2.10. Pregnant or breastfeeding
- 4.2.11. Laboratory values obtained within 45 days prior to study entry:
 - LDL-c <80 mg/dl while not on statin or LDL-c <60 mg/dl while on statin
 - ALT > 3 x Upper Limit of Normal (ULN)
 - AST > 3 x ULN
 - Creatinine kinase (CK) > 10 x ULN
 - Calculated creatinine clearance (CrCl) <50 mL/min, as estimated by the Cockcroft-Gault equation
- 4.2.12. Life expectancy <12 months
- 4.2.13. Prior organ transplant
- 4.2.14. Active malignancy
- 4.2.15. Inflammatory muscle disease

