4.3 Study Enrollment Procedures

4.3.1 Prior to implementation of this protocol, sites must have the protocol and the protocol consent form approved by their local institutional review board (IRB).

Once a candidate for study entry has been identified, details will be carefully discussed with the subject. The subject will be asked to read and sign the approved protocol consent form.

Candidates for study entry will be identified using an existing IRB-approved data repository of HIV-infected persons in the Northwestern Medicine Enterprise Data Warehouse (NMEDW). These candidates will be identified by querying this NMEDW data repository for any living HIV-infected persons aged 18 to 75 who have no HIV viral RNA values of 400 copies/ml or greater anytime in the previous 12 months from the time of screening and who have any diagnosis of coronary heart disease (CHD) based on any documented ICD-9-CM codes 410-414 and/or ICD-10-CM codes I21-I25. Candidates will also be identified by calculating the 10-year ASCVD risk of patients referred by primary care providers. Once these candidates are identified, participants will be excluded if they are noted to be prescribed atorvastatin 20mg daily or greater, rosuvastatin 10mg daily greater, atazanavir/ritonavir (at any dose), lopinavir/ritonavir (at any dose), simeprevir.(at any dose), or are not currently taking antiretroviral therapy. Of the remaining candidates, persons with an active primary care provider and/or infectious disease provider at Northwestern Medicine will be eligible to be contacted for enrollment via telephone. The order of contacting patients will be by those with the most recent new diagnoses of CHD first, with the plan to continue contacting patients (those with the earlier CHD diagnosis dates would be contacted later, then patients with no known CHD but with 10-year ASCVD risk of 15% or greater) until the target enrollment is achieved.

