5.4 Concomitant Medications

Below are lists of selected concomitant medications. These lists are only current as of the date of this protocol. Therefore, whenever a concomitant medication or study agent is initiated or a dose changed, investigators must review the concomitant medications' and study agents' most recent package inserts, and Investigator's Brochures to obtain the most current information on drug interactions, contraindications, and precautions.

5.4.1 Required Medications:

All subjects should be maintained on the same antiretroviral medications throughout the entire study period, as medically feasible, with no introduction of new chronic therapies.

Standard therapy for HIV and care in the setting of CHD and/or high risk for ASCVD is allowed except for treatments noted in the exclusion criteria described above and as noted in the prohibited medications section below.

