5.4.2 Prohibited Medications

The following medications are prohibited during the study and administration will be considered a protocol violation.

- Atazanavir/ritonavir
- Lopinavir/ritonavir (Kaletra)
- Cyclosporine
- Rifampin
- Simeprevir
- Cholestyramine / aspartame
- Cholestyramine / sucrose
- Colesevelam
- Colestipol
- Prevalite
- Questran
- Questran Light
- Welchol
- Colestid
- Ezetimibe
- Zetia
- Liptruzet
- Vytorin
- Fenofibrate
- Fenofibric acid
- Gemfibrozil
- Antara
- Lipofen
- Lofibra
- Tricor
- Fenoglide
- Triglide
- Trilipix
- Fibrincor
- Lopid
- Icosapent ethyl
- Lomitapide
- Mipomersen
- Vascepa
- Juxtapid
- Kynamro
- Niacin
- Niaspan
- Simcor
- Niacinamide
- Simvastatin

- Fluvastatin
- Lovastatin
- Cerivastatin
- Atorvastatin
- Pitavastatin
- Advicor
- Altocor
- Altoprev
- Atorlip
- Baycol
- Caduet
- Canef
- Inegy
- Lescol
- Lipex
- Lipitor
- Lipobay
- Lipostat
- Lipvas
- Mevacor
- Pitava
- Selektine
- Simcard
- Simcor
- Simlup
- Sortis
- Torvacard
- Torvast
- Totalip
- Tulip
- Vytorin
- Zocor

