7.2 Requirement for Precautionary or Prohibited Medications (see PSWP)

Subjects who need to initiate therapy with erythromycin, colchicine, cyclosporine, or rifampin should be asked to hold study drug. If use of one of these precautionary medications is anticipated to be short-term, the site investigator may consider restarting study drug after use of prohibited medication is discontinued.

Subjects who begin a statin medication provided through clinical care should discontinue study drug. Taking two statins can increase the risk of toxicity.

Subjects who temporarily or permanently discontinue study treatment will be followed on study, off treatment through the study termination visit with subject evaluations as per section 6.2.4.

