8.0 CRITERIA FOR DISCONTINUATION

8.1 Permanent Study Treatment Discontinuation

- Drug-related toxicity requiring permanent study treatment discontinuation (see section 7.0)
- Requirement for prohibited concomitant medications (see section 5.4)
- Pregnancy
- Breast-feeding
- Completion of treatment as defined in the protocol
- Request by subject to terminate treatment
- Clinical reasons believed life threatening by the physician, even if not addressed in the toxicity section of the protocol
- Failure by the subject to attend 2 consecutive clinic visits

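### Exclusion criterion 4.2.4 is worded the wrong way round: it excludes candidates on neither cyclosporine nor rifampin and does not exclude those taking one, contradicting Sections 5.4.1 and 5.4.2

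*Combined protocol and SAP*

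**What the plan says.** Under the heading "4.2. Exclusion Criteria", item 4.2.4 reads "Not currently receiving any of the following agents: cyclosporine or rifampin". The item just before it, 4.2.3, opens with the same words: "Not currently receiving antiretroviral therapy or taking any of the following antiretroviral agents: atazanavir/ritonavir, lopinavir/ritonavir, or simeprevir".

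Four later sections deal with the same two drugs, by name or by cross-reference:

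- **Section 5.4.1** allows standard HIV and cardiovascular care "except for treatments noted in the exclusion criteria described above" and those in the prohibited list.
- **Section 5.4.2** introduces that list with "The following medications are prohibited during the study and administration will be considered a protocol violation". Cyclosporine and rifampin are both on it.
- **Section 7.2** says "Subjects who need to initiate therapy with erythromycin, colchicine, cyclosporine, or rifampin should be asked to hold study drug".
- **Section 8.1** includes the need for a prohibited medication among the grounds for permanently stopping study treatment.

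Section 4.3.1 describes the record screen used before candidates are telephoned. It names certain statin doses, three antiretroviral or antiviral agents and absence of ART. It does not mention cyclosporine or rifampin.

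**The concern.** An exclusion list has one rule: if the statement is true of the candidate, the candidate is excluded. Item 4.2.4 is phrased as an inclusion criterion would be, but it sits in the exclusion list, so its effect is reversed.

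The item has a safety purpose. The trial's rationale (Sections 2.1 and 3.0 onward) is built around statin drug interactions, and these are two drugs that the protocol does not allow alongside study treatment. Eligibility items are commonly copied into a checklist and audited one by one. Copied faithfully, this one gives the wrong answer for every candidate. Two things follow: screening-failure and deviation records become unclear, because correctly enrolled subjects appear to meet an exclusion; and the one criterion that names these drugs does not bar their users.

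**Working it through.** No arithmetic applies and the plan gives no figure to reproduce. The check is to apply the exclusion rule to each kind of candidate and compare the result with Section 5.4.2.

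| Candidate's current medication | Is the 4.2.4 statement true? | Result under 4.2.4 as written | Status under 5.4.2 if medication is unchanged |
|---|---|---|---|
| Neither drug | Yes | Excluded | Compliant |
| Cyclosporine only | No | Not excluded by this item | Protocol violation |
| Rifampin only | No | Not excluded by this item | Protocol violation |
| Both drugs | No | Not excluded by this item | Protocol violation |

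The two rules disagree in every row. Passing 4.2.4 requires taking at least one of the drugs; complying with 5.4.2 requires taking neither. The set of candidates who satisfy both is empty. Conversely, every subject who complies with 5.4.2 from entry meets 4.2.4 and so technically meets an exclusion criterion. That is all properly enrolled subjects, whatever the final enrolment number.

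**Which direction was meant.** Section 5.4.1 refers back to the exclusion criteria as a source of disallowed treatments. That makes sense only if 4.2 bars users. Sections 5.4.2, 7.2 and 8.1 all treat the drugs as incompatible with study treatment. Item 4.2.4 stands alone against four sections.

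**Whether the wording could be read otherwise.** In 4.2.3 the opening 'Not' is correct: people off ART are excluded, and the sentence then switches to 'taking' for the listed agents. A reader must therefore apply the opening words literally in 4.2.3 and disregard them in 4.2.4. The phrase may have been carried over from one item to the next, but that is an inference.

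**What else could stop a user at entry.**

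- Section 6.1 schedules medication history at screening and concomitant medication review at screening and week 0.
- Section 6.3.3 requires prescription drugs from the 30 days before entry to be recorded.
- Sections 5.4 and 5.4.3 call for an interaction review when a study agent is started, which happens when run-in pravastatin begins.
- Item 4.2.13 excludes prior organ transplant and may catch some cyclosporine users. Item 4.2.6 excludes an absolute contraindication to statins and might be applied by a careful investigator.

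None of these states that current use of cyclosporine or rifampin excludes a candidate. Item 4.2.4 is the only eligibility criterion that names them.

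**The case against.** The best defence is that nobody would follow the literal text. It would admit only users of prohibited drugs, so the slip would surface with the first candidate, and staff would apply the evident intent. Medication is reviewed twice before dosing, and a user who did enter would be in violation under 5.4.2 from the first day of run-in. Nothing statistical depends on the item. All of that stands, and it limits the weight of the point. It does not remove the contradiction: the governing entry rule says the opposite of the sections it is meant to serve.

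Three stronger readings are tempting, and the documents do not support them.

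- **That 4.2.4 is the only check at entry, so users have no other stop.** The medication reviews, 4.2.13 and 5.4.2 are partial stops. The accurate statement is only that no other criterion names the drugs.
- **That the record screen in 4.3.1 has a gap of its own.** It says "participants will be excluded if they are noted to be prescribed atorvastatin 20mg daily or greater" and goes on to a short list, but it is a pre-contact filter. It also omits statin intolerance, kidney disease, ejection fraction, transplant, malignancy and the laboratory limits. Omitting these two drugs is not an error.
- **That 4.2.3 is defective too.** It is correct as written, and 4.3.1 restates its content clearly.

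**Conclusion.** The point holds. Item 4.2.4 is inverted in the current text and contradicts Sections 5.4.1, 5.4.2, 7.2 and 8.1. On paper the reversal is complete: it gives the wrong answer for every candidate. In practice the effect is probably small, because the intent is recoverable and other checks exist. The documents give no count of candidates taking either drug, so the number exposed cannot be estimated, and a reader should not infer that users would in fact be enrolled.

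The conclusion rests on two assumptions: that meeting an item under the exclusion heading excludes the candidate, and that 5.4.1 and 5.4.2 express the protocol's intent. The consequences fall on eligibility checking, screening-failure records and deviation classification. Sample size, power, endpoints and analysis are untouched. It should be corrected because it is an operative rule with a safety purpose and the correction is nearly free.

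**What to change.** Reconcile 4.2.4 with 5.4.1 and 5.4.2 by deleting the inverted 'Not', so that current receipt of either drug is the excluding condition and the entry criterion points the same way as the prohibited-medication list. Carry the same wording into the eligibility checklist, and check whether any checklist or screening-failure form already in use copied the inverted text.

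The cost is a one-word protocol correction and a checklist update, with no effect on recruitment targets or analysis. No change to 4.3.1 or 4.2.3 is needed.

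Separately, 7.2 (hold, with possible restart after short-term use) and 8.1 (permanent discontinuation) give different consequences when one of these drugs is needed during the study. Those two sections must also be reconciled; this review takes no position on how.
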